### 3 STUDY ENDPOINTS

#### 3.1 Primary Endpoints

- The primary endpoint is PFS, based on central radiological assessment per mRECIST, version 1.1, in patients with advanced GIST. Progression-free survival is defined as time from randomization to disease progression, or death due to any cause, whichever occurs first.

#### 3.2 Secondary Endpoints

The key secondary endpoints are:

- Objective response rate defined as the percentage of patients whose best response is CR or PR as assessed by central radiology using mRECIST, version 1.1.
- Overall survival defined as the time from date of randomization to death due to any cause.

Additional secondary endpoints include:

- All individual EORTC QLQ-C30 scores, eg, physical functioning score, pain score, role functioning score, appetite loss score, etc.
- Adverse events, serious AEs (SAEs), and changes in safety laboratory parameters, 12-lead ECG evaluations, and ECOG PS. The intensity of AEs will be assessed by the NCI CTCAE, version 5.0.
- Response as assessed by Investigator per mRECIST, version 1.1. and assessed by central radiology per Choi criteria.
- Disease control is defined as the rate of CR, or PR of any duration, or SD lasting for at least 16 weeks per mRECIST, version 1.1.
- Duration of response defined as the time from first documentation of tumor response to disease progression or death due to any cause.
- Plasma drug concentration at specified time points.
- Abdominal pain as measured by a numeric rating scale (0-10).

■ [REDACTED]

[REDACTED]

■ [REDACTED]

## 4 STUDY PLAN

### 4.1 Study Design

This is an open-label, randomized, Phase 3 study in patients with locally advanced unresectable or metastatic GIST (advanced GIST) of avapritinib versus regorafenib in patients previously treated with imatinib and 1 or 2 other TKIs.

All study visits are intended to be conducted on an outpatient basis. After provision of written informed consent, patients will be evaluated for study eligibility during the screening period within 4 weeks (28 days) before study drug administration on Cycle 1 Day 1 (C1D1). During the screening period, eligibility will be confirmed; management of baseline concomitant conditions will be recorded and stabilized; and baseline symptoms will be assessed. Hematology, blood chemistry, mutation status, brain imaging (CT scan or MRI), and baseline tumor assessments (CT scan or MRI) will be performed within 28 days of C1D1.

Patients are to be randomly assigned, in a 1:1 ratio, to 1 of 2 treatment arms: Arm A (avapritinib) or Arm B (regorafenib) stratified by TKI treatment (third vs. fourth), geographic region (Asia vs. rest of the world), and PDGFR $\alpha$  D842V mutation status measured in ctDNA or a tumor sample (PDGFR $\alpha$  D842V mutation present vs. absent). Patients randomized to Arm A will receive avapritinib 300 mg PO QD. Patients who experience disease progression on avapritinib, based on central review, will be offered the opportunity to continue taking treatment with avapritinib if there is no symptomatic evidence of disease progression or laboratory abnormalities attributable to disease progression, no rapid progression of disease or a progressive tumor requiring urgent alternative medical intervention at critical anatomical sites, and no decline in ECOG PS. Patients randomized to Arm A must consent to continue avapritinib treatment after disease progression; see [Section 7.7](#) for additional details.

Patients randomized to Arm B will receive regorafenib 160 mg PO QD for 3 weeks out of every 4-weeks (28 days) cycle (ie, 3 weeks on/1 week off). Patients who experience disease progression on regorafenib, as confirmed by central radiology review, may be offered the opportunity to cross over to the avapritinib treatment arm (Arm A); see [Section 7.6](#) for additional details. Prespecified dose modification guidance for AEs related to regorafenib and to avapritinib are described in [Section 6.3.1](#).

At least 70% of the patients enrolled should be receiving the study drug as their third distinct TKI treatment for GIST, ie, no more than 30% of patients should be receiving the study drug as their fourth distinct TKI treatment for GIST. In addition, patients will

receive BSC, excluding any additional anticancer therapy such as any systemic antineoplastic therapy (including kinase inhibitors and chemotherapy), radiation therapy, or surgery.

All patients will present to the study center on C1D1 for the first dose of study drug, vital sign measurements, physical exam, quality-of-life (QoL) assessment, PRO assessments, laboratory assessments, ECG and AE recording. In Cycle 2 Day 1 (C2D1), Cycle 3 Day 1 (C3D1), Cycle 4 Day 1 (C4D1) and Cycle 5 Day 1 (C5D1), patients will present to study centers for physical examination, vital signs measurements, laboratory assessments, QoL assessments, PRO assessments, ECG, and AE/concomitant medication recording. On C1D15 and C2D15, all patients will attend study center visits for vital sign measurements, serum chemistry measurements, and AE reporting. For all subsequent cycles, all patients will attend study center visits every other cycle on Day 1 of odd cycles (ie, C7D1, C9D1 etc.) for physical examination, vital sign measurements, laboratory assessments, QoL assessments, PRO assessments, ECG and AE recording. At any point in time between treatment cycles patients should attend or contact the study center for AE reporting, evaluation, and medical intervention.

[figure not shown]
Tumor assessments will be performed at Baseline and then every 8 weeks ( $\pm$  1 week) counting from C1D1, regardless of the scheduled treatment cycles, ie, if study treatment is interrupted or discontinued for any reason, tumor imaging should continue according to an 8-week schedule until tumor progression is confirmed by central radiology review. Computed tomography with intravenous (IV) contrast is the preferred imaging modality, unless a site of disease is better evaluated by MRI.

It is anticipated that patients will receive at least 1 cycle of avapritinib if randomized to Arm A and regorafenib if randomized to Arm B; no maximum treatment duration has been set. After C1, patients may continue to receive study drug until precluded by toxicity, noncompliance, pregnancy, withdrawal of consent, physician decision, PD, death, or closure of the study by the Sponsor.

All patients will attend an End-of-Treatment (EOT) visit within 14 ( $\pm$ 7) days after the last dose of study drug. A safety Follow-up visit for resolution of any ongoing AE will be made on Day 30 ( $\pm$ 7 days) after the last dose of study drug, or at the time the patient initiates another antineoplastic therapy. Patients who discontinue study treatment before disease progression will undergo tumor assessments every 8 weeks until disease progression, death, or patient withdrawal of consent. After documentation of disease progression by central radiology review, patients are to be followed for subsequent antineoplastic therapy and survival approximately every 2 months until death, withdrawal of consent or closure of the study by the Sponsor.

The expected enrollment period is approximately 18 months, and the expected duration of the study to reach the primary analysis timepoint is approximately 24 months until a total number of 264 PFS events are reached. The study will be completed when all patients are no longer receiving study drug and follow-up for OS has been concluded.

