### 4.2 Justification of the Study Design

The study is designed as a randomized, open-label, efficacy and safety study. Patients who meet all study eligibility criteria will be randomly assigned in a 1:1 ratio to receive avapritinib or regorafenib. Random assignment of patients minimizes bias and helps ensure that both known and unknown risk factors are distributed evenly between treatment groups. Eligible patients will continue to receive BSC throughout the duration of the study.

The study is not blinded because the distinct AE profiles of regorafenib and avapritinib make effective blinding impossible. In particular, regorafenib treatment is associated with palmar-planar erythrodysesthesia (PPE) in 67% of patients, rash in 30% of patients and hypertension in 59% of patients (Stivarga, 2017). In addition, the adverse events requiring dose modification are very different between regorafenib and avapritinib; therefore, appropriate patient care requires that the treating physician and patient know which drug is being used. In order to prevent bias in assessing efficacy endpoints, PFS and response will be determined by independent, central radiology reviewers blinded to treatment group, and the sponsor team responsible for analysis of the study will not have access to efficacy and safety data identified by treatment group.

Demonstration of the efficacy of avapritinib as assessed by PFS is the primary objective of the study. Response assessments used to determine PFS for the primary endpoint will be based on standard response criteria (mRECIST, version 1.1) evaluated by blinded central radiology review to ensure consistent tumor assessments between the 2 randomized treatment arms.

Key secondary endpoints including ORR and OS and additional secondary endpoints including safety, DCR, DOR, disease response by Choi criteria, EORTC-QLQ-C30 scores, plasma drug concentration and an abdominal pain assessment will provide

important supportive data to help determine whether avapritinib provides a clinically relevant improvement in outcome compared to regorafenib.

An Independent Data Monitoring Committee (IDMC) will be in place to review study progress including final primary efficacy outcomes, safety data, adherence to protocol, and follow-up assessments.

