#### **5.4 Patient Identification and Registration**

Patients who are candidates for enrollment into the study will be evaluated for eligibility by the Investigator to ensure that the inclusion and exclusion criteria (see [Section 5.2](#) and [Section 5.3](#)) have been satisfied.

Upon identification of an eligible patient, study centers will submit a request to the Sponsor or designee to register each patient for enrollment. Further instructions will be provided in the study manual.

The Medical Monitor or designee will confirm eligibility for all patients before randomization and administration of the first dose of study drug.

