- Abbreviations: AE = adverse event; C = cycle; CT = computed tomography; ctDNA = circulating tumor deoxyribonucleic acid; D = day; ECG = electrocardiogram; ECOG PS = Eastern Cooperative Oncology Group Performance Status; EORTC-QLQ-C30 = European Organisation for Research and Treatment of Cancer Quality of Life Questionnaire; EOT = End-of-Treatment; EQ-5D-5L = EuroQol 5 Dimension Questionnaire; F/U = follow-up; FACT-Cog = Functional Assessment of Cancer Therapy-Cognitive Function; GIST = gastrointestinal stromal tumor; IV = intravenous; MRI = magnetic resonance imaging; PD = progressive disease; PFS = progression-free survival; MRI = magnetic resonance imaging; PGI-C = Patients' Global Impression of Change; PGI-S = Patients' Global Impression of Severity; PK = pharmacokinetics; SAE = serious adverse event; ULN = upper limit of normal.
- a On days when study drug is to be administered in the clinic, all tests or procedures must be completed pre-dose at each study visit unless otherwise indicated. Additional safety tests (eg, hematology, ECG) may be performed whenever clinically indicated, at the Investigator's discretion. Whenever a test result is questionable, it should be repeated immediately.
  - b Patients receiving regorafenib who experience disease progression documented by central radiology review may be permitted to cross over to receive treatment with avapritinib after disease progression confirmed by central radiology review (see [Section 7.6](#)) and a washout period of 7 to 28 days after their last dose of regorafenib. At the first study visit after the washout period, the patient will complete the C1D1 assessment schedule except for the following tests, which are not required: PK blood sample and biomarker plasma sample. After patients cross over to treatment with avapritinib, ECGs will be performed following the same schedule as prior to cross over and AEs will only be assessed for their relationship to avapritinib.

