- s Liver function tests (ALT, AST, alkaline phosphatase, total bilirubin (direct bilirubin if total is > ULN) should be measured every 4 weeks. On even-numbered cycles, when a study visit is not required, these tests should be done locally, and any clinically significant abnormalities should be entered as adverse events, and laboratory values should be entered in unscheduled laboratory eCRF.
- t Tumor imaging will be done at Screening and then every 8 weeks ( $\pm$  1 week) from Cycle 1 Day 1 until disease progression and will be assessed by central radiology review. Disease response assessments using the Choi criteria will be performed centrally. Note that tumor imaging should occur every 8 weeks regardless of the scheduled treatment cycles ie, if study treatment is interrupted or discontinued for any reason, tumor imaging should continue according to an 8-week schedule until disease progression or death. Computed tomography (CT) with IV contrast of the chest and CT or MRI with IV contrast of the abdomen and pelvis will be performed. CT of the chest is not required after screening unless there were sites of disease in the chest. CT with IV contrast is the preferred imaging modality, unless a site of disease is better evaluated by MRI. If a patient is not tolerant of IV contrast, non-contrast scans may be performed. For each patient, the same method of tumor imaging used at baseline should be used throughout the study.
- u Brain imaging should be performed at Screening, Week 12 ( $\pm$ 1 week), and Week 24 ( $\pm$ 1 week), and should be repeated as clinically indicated, ie, for unexpected neurologic AE. Patients who have been on study for more than 12 weeks should have imaging performed at the next scheduled visit and 12 weeks later ( $\pm$ 1 week).
- v The EORTC-QLQ-C30, [REDACTED] will be completed at scheduled clinical site visits up to EOT. The questionnaires are not required at the EOT visit or after cross-over.
- w Adverse events are to be recorded from the start of study drug administration through the Safety Follow-up Assessment.
- x Serious AEs and concomitant medications are to be recorded from the date of the informed consent signature through the Safety Follow-up Assessment.

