## 7 DESCRIPTION OF STUDY PROCEDURES

### 7.1 Screening

After informed consent, all patients will undergo screening procedures within 28 days before dosing on C1D1 to determine eligibility. Patients may be randomized in the system at any time but must be dosed within 28 days of signing of informed consent.

The following procedures will be performed at the Screening visit:

- Obtain demographic data, including sex, date of birth/age, race, and ethnicity;
- Complete medical history, including a history of GIST and/or other malignancies, prior treatments, the response to each treatment if available, and concurrent illnesses;
- Complete physical examination and a basic neurological assessment, including ECOG PS;
- Vital signs including weight, temperature, pulse, and systolic/diastolic blood pressure. Height will also be measured at Screening;
- 12-lead ECG;
- Obtain plasma sample for exploratory biomarkers and ctDNA mutation testing;
- Clinical laboratory assessment (hematology, coagulation, serum chemistry, and urinalysis);
- Serum pregnancy test (women of childbearing potential only);

- Tumor imaging by CT with IV contrast or MRI (CT is required for the chest and preferred for all body regions unless a site of disease is better imaged by MRI). If a patient is intolerant of IV contrast, CTs may be performed without IV contrast.
- Brain imaging by MRI or CT (MRI is preferred, if available);
- Recording of concomitant medications and SAEs. Concomitant medications and SAEs are to be collected from the date of the informed consent signature through the Safety Follow-up Assessment, while AEs are to be collected from start of study drug administration through the Safety Follow-up Assessment.

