### **7.5.3 Quality-of-Life Instruments**

Patients will complete the EORTC-QLQ-C30 at scheduled clinical site visits up to the EOT visit, as outlined in Table 2. These assessments are provided in Appendix 8 (EORTC-QLQ-C30).

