**3.2.5 Baseline and Rebaseline Values**

Baseline is defined as the last observation prior to first dose of study drug, i.e., the Day 1 pre-dose value or the last available (including unscheduled) value before Day 1 if a Day 1 pre-dose value is unavailable. For summaries using the ITT Population, patients who were randomized but did not receive study drug will be baselined at their last available observation.

Rebaseline is defined as the last observation prior to first dose of avapritinib in the extended study treatment period. For summaries using the ITT Population, patients who signed informed consent to crossover to avapritinib post-disease progression but did not subsequently receive study drug will be re-baselined at their last available observation. Patients who are initially randomized to avapritinib will not be rebaselined for continuation to avapritinib post-disease progression.

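### The only scheduled baseline QLQ-C30 is on C1D1, and no rule requires it before randomization or disclosure of the arm in this open-label trial

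*Protocol*

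**What the plan says.** **Collection.** Protocol Section 4.1 places the first quality-of-life form "on C1D1 for the first dose of study drug, vital sign measurements, physical exam, quality-of-life (QoL) assessment". Section 7.5.3 refers the schedule to Table 2: "Patients will complete the EORTC-QLQ-C30 at scheduled clinical site visits up to the EOT visit, as outlined in Table 2". In Table 2 the QLQ-C30 row is empty under Screening and first marked at C1D1. The list of screening procedures in Section 7.1 names no questionnaire.

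**Order relative to dosing.** Footnote a of Table 2 says that, on days of dosing in the clinic, "all tests or procedures must be completed pre-dose at each study visit unless otherwise indicated". The C1D1 form is therefore pre-dose.

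**Order relative to randomization.** Section 5.4 states: "The Medical Monitor or designee will confirm eligibility for all patients before randomization and administration of the first dose of study drug". Section 7.1 adds: "Patients may be randomized in the system at any time but must be dosed within 28 days of signing of informed consent". Neither section places the questionnaire before or after randomization.

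**Blinding.** Section 4.2 states: "The study is not blinded because the distinct AE profiles of regorafenib and avapritinib make effective blinding impossible".

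**Analysis.** SAP 3.2.5 states: "Baseline is defined as the last observation prior to first dose of study drug". Protocol Section 10.5.3.2.3 compares mean change from baseline to Week 12 between arms by t-test for all individual scores. SAP 4.6.3.6 applies that test to physical functioning, pain, role functioning and appetite loss, and includes only patients with a baseline form.

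**The concern.** QLQ-C30 scores are self-reported and can respond to expectation. In a randomized comparison of change scores, the baseline should be a quantity that assignment cannot have affected. Both documents tie baseline to the first dose. That protects it from the drug's effects but not from knowledge of which drug is coming. A site can follow the plan exactly and still collect a baseline from a patient who already knows the arm. For PFS and response, Section 4.2 answers the open-label problem with blinded central review. The questionnaire has no comparable safeguard, although protecting its baseline would be easy. At stake is how the between-arm QLQ-C30 comparison, a named secondary objective, can be interpreted.

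**Working it through.** The plan gives no figure to reproduce. The point rests on timing, so I set the provisions side by side and then worked out what they imply for the contrast.

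**1. Is there any earlier form?** No. Table 2 and Section 7.1 schedule none at Screening. Footnote o lets tests from the 7 days before the first dose stand in for C1D1, but it covers safety laboratory tests and pharmacodynamic samples and is not attached to the questionnaire row. Section 4.1 mentions assessing baseline symptoms during screening, but schedules no QLQ-C30 for that purpose.

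**2. Can randomization precede the form?** Yes. Randomization must precede the first dose but is not tied to a day. The 28-day limit runs from consent to dosing. It is only an outer bound on the gap between randomization and C1D1, because eligibility and D842V status must be known first.

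**3. Can the form precede randomization?** Also yes. A patient randomized on C1D1 could complete it beforehand. The order on that day is not stated.

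**4. Effect on the contrast.** Let b0 be the between-arm shift in mean score at C1D1 caused by knowing the arm, and b12 the corresponding shift at Week 12.
- Change score with an arm-aware baseline: bias = b12 − b0.
- Change score with a pre-randomization baseline: bias = b12.
- Regression on an arm-aware baseline with within-arm slope β: bias = b12 − β·b0. Adjustment therefore does not remove b0, because assignment has affected the covariate itself.

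**5. Sensitivity of the t-test to a net shift, on assumed values only.** The documents give no standard deviation (SD) for QLQ-C30 change and no shift. Let d be the absolute value of b12 − b0, in points on the 0 to 100 scale. With no true effect and n patients per arm, SE = SD × √(2/n), and the two-sided rejection rate at nominal 5% is Φ(d/SE − 1.96) + Φ(−d/SE − 1.96).

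Example: n = 230 and SD = 25 give SE = 25 × √(2/230) = 2.33. For d = 2, d/SE = 0.86 and the rate is 13.8%.

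The planned arm size is 230. The 150 allows for fewer patients at Week 12 and is assumed, as are the SDs and d.

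| n per arm | SD | d = 0 | d = 1 | d = 2 | d = 5 |
|---|---|---|---|---|---|
| 230 | 20 | 5.0% | 8.4% | 18.9% | 76.5% |
| 230 | 25 | 5.0% | 7.1% | 13.8% | 57.3% |
| 230 | 30 | 5.0% | 6.5% | 11.0% | 43.2% |
| 150 | 20 | 5.0% | 7.2% | 13.9% | 58.1% |
| 150 | 25 | 5.0% | 6.4% | 10.7% | 41.0% |
| 150 | 30 | 5.0% | 6.0% | 8.9% | 30.3% |

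The table shows how the test would respond to a given net shift. It is not evidence that a shift exists.

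**The case against.** **The shift may persist and cancel.** Week 12 is also open label. If b12 = b0, the change score is unbiased with an arm-aware baseline, while a pre-randomization baseline leaves b12 in the contrast. This stands: moving the form does not remove expectation at Week 12 and could increase bias in the change score. However, cancellation needs two unmeasured shifts to be equal, which nobody can check. With a pre-randomization form the baseline is comparable by randomization, and the only reporting bias left is the one that any open-label Week 12 score carries.

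**C1D1 is closer to treatment.** Exclusion criterion 4 bars systemic anticancer therapy only in the week before the first dose, so a screening form may reflect the toxicity of a prior drug. This also stands, but randomization balances it in expectation, so it costs precision rather than validity.

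**Stronger readings that the documents do not support.**
- A reader might infer that every baseline is completed after randomization. The order on C1D1 is unspecified, so only some forms need be affected.
- A reader might infer from the different food instructions in Section 6.3 that patients know their arm before completing the form. That section says how each drug is taken, not when the patient is told.
- A reader might see selection bias because randomized patients who are never dosed lack a baseline form. SAP 3.2.5 baselines such patients at their last available observation, and no on-treatment form is scheduled for them, so a screening form would not bring them into the Week 12 comparison.
- A reader might extend the point in full to abdominal pain. Its schedule is partly redacted and SAP 4.6.3.7 plans only descriptive summaries.

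**Conclusion.** The gap is real but modest. The only scheduled baseline QLQ-C30 is at C1D1, pre-dose, and neither document requires it before randomization or disclosure, so baseline scores may be given with knowledge of the arm. A shift present at baseline but not to the same extent at Week 12 would bias the planned t-test, and baseline adjustment would not remove it. Neither its size nor its direction can be derived from the documents. The conclusion assumes that some patients are told their arm before completing the form, which the plan permits but does not require. SAP 4.6.1 confines the gatekeeping to PFS, ORR and OS, so no primary or key secondary inference is affected. This is a cheap improvement to an additional secondary endpoint.

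**What to change.** - **Protocol Table 2 and Section 7.1:** require the QLQ-C30 after consent and before randomization, as close to randomization as practical. Include the abdominal pain scale if it follows the same schedule.
- **SAP 3.2.5:** define questionnaire baseline as the last form completed before randomization, with the C1D1 pre-dose form as fallback.
- **Patients already enrolled:** compare form and randomization dates and times, report how many forms came first, and run a sensitivity analysis restricted to forms completed before randomization.

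**Cost.** One form at a visit that already takes place. The baseline is somewhat older and may reflect prior therapy, and some screen failures complete a form. Introduced mid-trial, the change creates two baseline definitions by enrollment date. SAP 4.7.1 refers to patients enrolled before amendment 2, so this applies here, and the sensitivity analysis is the part that covers those patients.
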